Participants in this study will undergo a great number of procedures in a relatively short period of time. All of the procedures that are to be performed in this study are standard research measurements, with well-defined risks and discomforts. No particular measurement or procedure is exceedingly burdensome, however the cumulative burden of undergoing all of these procedures is significant. This burden is a reasonable one, as it is the intent of this study to induce fatigue and PEM in its participants. However, PI-ME/CFS patients are defined by their vulnerability to exhaustion. It is probable that some participants will be unable complete the entire study. Some participants may also be so exhausted by the study that they may require some time to recover prior to travelling home. Thus, the study team will be solicitous of the participants in regard to their comfort and flexible to provide for their needs.

This 'Phase I' study will analyze the collected data in an exploratory manner. The goal of these analyses is to identify physiological alterations for the purpose of hypothesis generation. A broad array of laboratory methods that query different aspects of human physiology will be performed on collected samples. The protocol is looking for positive results that would generate testable hypotheses and for negative results that will provide a sense of the biological measurements and physiological mechanisms where large differences are unlikely to be seen with future study. De-identified data and biological samples will be shared with a wide range of collaborators, both within NIH and across the world. A larger 'Phase II' study is planned that will use these results to determine potential mechanisms for intervention and estimate effect sizes for larger clinical and interventional studies.

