If the overall multivariate test is significant, we will follow up with several post-hoc tests. Specifically, we will first conduct multivariate tests to compare the adjudicated PI-ME/CFS group (i.e. participants determined to have PI-ME/CFS by the protocol's adjudication process) vs the other two control groups, and the PI-ME/CFS group vs each of the two control groups. These analyses will initially performed using only HV and COVID-19 HV participants meeting all inclusion and exclusion criteria. As noted above, for analyses that are statistically significant, the analysis will be repeated using all HV and COVID-19 HV participants that did not report substantial clinical fatigue to determine if the results remain statistically significant when less stringent inclusion/exclusion criteria are applied.

Second, univariate ANOVA will be used for both cross-sectional measurements and pre and post exercise measurements separately to identify differences among groups. A
similar univariate analysis will be conducted for the measurements of change from pre- to post exercise using the univariate ANOVA.

Additionally, descriptive statistics will be used to characterize the entire group of ME/CFS participants that completed the phenotyping evaluation regardless of adjudication. Comparisons will be made between the adjudicated PI-ME/CFS group and the phenotyping ME/CFS group. If there is no significant difference between the above two groups, it is not necessary to compare a ME/CFS group to our two control groups. Where statistically appropriate, the ANOVA methods described above will be used to compare the ME/CFS group with the two control groups.

Statistical approaches such as chi-square tests and multinomial logistic regression models will be used to examine the group differences for categorical outcomes.

A level of significance is set at 0.05. Multiple comparison test procedures such as Bonferroni and Dunnett's methods will be used to examine the differences in each outcome measure among groups.

The primary MRI imaging aim is to test whether PI-ME/CFS group has significantly different connectivity patterns compared to the HV control group.

To this end, functional MRI measures will be taken at three conditions: 1) performing a force task, 2) performing a cognitive task, to define a network of interest, and 3) at rest to compute functional connectivity. At each condition, fMRI will be measured at two time points: pre exercise (preEx) and post exercise (postEx).

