
We will use a multivariate regression model where the response variable is connectivity strength among regions of interest pre- and post- exercise. Predictors include group status and fatigue scores.

Region of interest for the connectivity analysis will be defined based on tasks 1) and 2). For this, data will be pre-processed with standard techniques using AFNI. Imaging quality assurance will be performed (i.e. motion correction parameters). We will fit a multivariate regression model to detect the differences in activity patterns of each task. Behavior and scales of fatigue will be entered as covariates.

Significance of the results will be set at p = 0.05 corrected for multiple comparisons for all analyses.

Lastly, we will conduct receiver operating characteristic (ROC) analysis for selected markers that are potentially important, which will be identified by exploratory analysis and several statistical approaches mentioned above. We will evaluate the accuracy of each marker for its ability to classify subjects in the PI-ME/CFS group from those in the HV control group. For example, if MRI imaging measurements are significantly different among groups, next, we will calculate the nonparametric area under the ROC curve (AUC) for each imaging marker and its 95% confidence interval.

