Each Working Group will begin by performing a literature review of their topic to ascertain the state of the ME/CFS field and guide their analyses. Analyses will be performed to both interrogate published findings to determine reproducibility and to make novel insights. Group members will first analyze the data that they are responsible

CNS IRB Protocol Template (2.5.15)

for collecting as part of the protocol. These individual data analyses will each be appropriate for the type of data collected and performed by Working Group members with experience in analyzing the data. Each Working Group will meet periodically to present their findings to each other, discuss issues of honing analyses, the need to expand data collection or perform additional experiments, identify areas of data consilience, and assemble a general consensus of how to interpret the results.

Once each Working Group completes its analysis and evaluation of the data, a series of combined Working Group meetings will be convened. Each Working Group will present their methods and results to each other. Break-out sessions will be organized that will mix the members of the Working Groups together to discuss how findings in one domain may relate to those in other domains. An open discussion for all Working Group members will be conducted to discuss issues of honing analyses, the need to expand data collection or perform additional experiments, identify areas of data consilience, and assemble a general consensus of how to interpret the results.

With the analyses of each Working Group completed, the research team will identify computational biologist collaborators to determine how to appropriately apply network analytics and machine learning approaches to the combined dataset. The goal of such analysis would to be elucidate observable linkages between the four research themes. These linkages would be areas of high interest in generating new hypotheses and also suggest potential therapeutic targets for future interventional studies.

These Working Groups have already been initiated to perform an interim analysis on the ME/CFS and HV cohorts completed as of October 2020.

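### ROC markers are picked from this study's own group comparisons and given an AUC and 95% CI in the same participants, with no validation or optimism correction

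*Combined protocol and SAP*

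**What the plan says.** Section 12.1 ends with a ROC step for "selected markers that are potentially important, which will be identified by exploratory analysis and several statistical approaches mentioned above". Its worked example is sequential: once imaging measurements differ significantly between groups, "we will calculate the nonparametric area under the ROC curve (AUC) for each imaging marker and its 95% confidence interval". The contrast is PI-ME/CFS against the HV group.

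The preceding approaches allow several routes to selection:
- an omnibus gate: "If the overall multivariate test is significant, we will follow up with several post-hoc tests";
- marker-by-marker tests: "univariate ANOVA will be used for both cross-sectional measurements and pre and post exercise measurements separately to identify differences among groups";
- an imaging regression in which "Predictors include group status and fatigue scores";
- a multiplicity rule with no named method or family size: "Significance of the results will be set at p = 0.05 corrected for multiple comparisons for all analyses".

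Section 12.3 adds judgement, since the Working Groups meet to "discuss issues of honing analyses, the need to expand data collection or perform additional experiments, identify areas of data consilience".

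Section 12 gives no hold-out set, cross-validation, bootstrap correction or external cohort for this step. The nearest check is the repeat of positive analyses in all participants (Section 12.1). That set contains the participants who produced the positive result, so it is not independent.

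**The concern.** A marker chosen because the groups differ in this sample has, by construction, an AUC pushed away from 0.5 in this sample. An interval computed as if the marker had been named beforehand ignores that, so a nominal 95% interval does not cover 95% of the time. Nothing in the text labels these AUCs as apparent.

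The study calls itself exploratory throughout, which limits the harm. But Section 4.1 says the planned Phase II study "will use these results to determine potential mechanisms for intervention and estimate effect sizes for larger clinical and interventional studies", and Section 12.2 makes a similar statement. Neither names AUCs for this use, and neither rules them out. An inflated AUC carried forward would give a follow-up study that is too small, or a claim of diagnostic accuracy that new patients do not bear out.

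**Working it through.** **Inputs from the documents.** Completion target 20 per group (Section 3.1); ceiling 50 per group (Section 12.2); significance level 0.05 (Section 12.1). The documents give no figure for AUC, interval width or coverage, so there is no figure of the plan's own to reproduce.

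**Assumptions.** Normal markers with standardised difference d; true AUC = Φ(d/√2), so d = 0, 0.5 and 0.8 give 0.50, 0.64 and 0.71. Mann-Whitney AUC, DeLong interval (AUC ± 1.96 SE), marker direction taken from the data. For the F test, the COVID-19 HV mean equals the HV mean. For the omnibus gate, Hotelling's test on 10 markers, with 5 of 10 real in the non-null cells. For the fatigue-adjusted test, groups 1.5 to 4 SD apart on fatigue.

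**Why selection alone does this.** At 20 per group a two-sided t test at 0.05 needs |t| > 2.024 on 38 df. The observed difference must therefore exceed 2.024 × √(2/20) = 0.64 SD. Under normality that is an AUC of Φ(0.64/√2) ≈ 0.67. Markers that pass will show an AUC of roughly this size or more, whatever the truth.

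**Simulation, 20 per group: mean AUC / coverage of the 95% CI**

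| Selection reading | True 0.50 | True 0.64 | True 0.71 |
|---|---|---|---|
| None | 0.57 / 94% | 0.64 / 94% | 0.71 / 93% |
| Omnibus gate, all markers reported | 0.60 / 82% | 0.66 / 91% | 0.72 / 93% |
| Fatigue-adjusted test, p<0.05 | 0.60–0.67 / 83–53% | 0.70–0.73 / 83–85% | 0.76–0.77 / 86–90% |
| Three-group F, p<0.05 | 0.66 / 48–51% | 0.71 / 87% | 0.745 / 92–93% |
| Two-group t, p<0.05 | 0.71 / 10–11% | 0.73 / 87% | 0.755 / 92–93% |
| Bonferroni, 10 tests | 0.77 / 0% | 0.79 / 55% | 0.80 / 85% |
| Bonferroni, 50 tests | 0.81 / 0% | 0.82 / 7% | 0.83 / 70% |
| Bonferroni, 200 tests | not run | 0.84 / 0.1% | 0.85 / 42% |

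The unselected null value of 0.57 comes from orienting the marker to the data, not from selection. The family sizes of 10, 50 and 200 are assumed. With correction few null markers pass, but only 9.7%, 3.5% and 1.4% of true-0.64 markers do, and those that pass are the overestimated ones. Even a true AUC of 0.80 shows 0.83, 0.85 and 0.86, with coverage 91%, 89% and 84%.

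**50 per group.** Null: 0.57 / 82% (omnibus), 0.60 / 53% (F), 0.63 / 15–17% (t). True 0.64: 0.64–0.67 with 91–95% coverage at p<0.05; 0.71 / 83% at p<0.001. True 0.71: 0.74 / 95% at p<0.001.

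**What it would do to a follow-up study.** Assumed route: d = √2 × Φ⁻¹(AUC), then a two-sided 0.05 t test with 80% power (noncentral t). Example: AUC 0.730 gives √2 × 0.613 = 0.867, hence 22 per group; with the true d = 0.5, 22 per group has 37% power.

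| Selection at 20 per group | True 0.64 (needs 64): suggested n, actual power | True 0.71 (needs 26): suggested n, actual power |
|---|---|---|
| Omnibus gate | 45, 65% | 25, 79% |
| Three-group F | 26, 42% | 20, 69% |
| Two-group t | 22, 37% | 18, 65% |
| p<0.001 (50 tests) | 11, 20% | 10, 40% |

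**Contrast with new data.** Markers selected at p<0.05 in 20 + 20 and re-estimated in an independent 20 + 20, direction fixed in advance, give AUC 0.500 with 94% coverage for a null marker and 0.639 with 94% coverage for a true 0.64.

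**The case against.** The strongest case is that the plan's only ROC example reads most naturally as a gate on the imaging family followed by an AUC for every imaging marker. That is the mildest row of the table: for true AUCs of 0.64 and 0.71 the inflation is 0.01 to 0.03, and coverage is at most about three points below its unselected level. The 10–11% figure needs an uncorrected per-marker test, while the plan calls for correction. The study is openly hypothesis-generating, a larger study is planned, and Section 12.1 presents its methods as only some of those to be used. Using an AUC to size that study is an inference, since group-difference effect sizes are the more natural input.

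Some inputs are also soft. The F-test row depends on the COVID-19 HV mean; placing it midway gives 0.734 / 83% rather than 0.713 / 87% for a true 0.64, so the bias grows. That row also does not fit the pre/post-exercise imaging markers, because the COVID-19 HV group does not attend the exercise stress visit. The 1.5 to 4 SD fatigue separation has no source in the documents.

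These points stand as limits on size and consequence. They do not supply validation. Even the mildest reading leaves null markers at 82% coverage, and correction raises the bias in real markers that pass. An exploratory label does not make a nominal 95% interval cover 95%.

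**Conclusion.** The concern holds. As written, the plan selects markers and estimates their accuracy in the same participants, with no correction. The direction of the error is certain for null and weak markers; its size depends on how selection is read. At 20 per group and without multiplicity correction, a null marker's mean AUC runs from 0.60 to 0.71 and its coverage from 82–83% down to 10–11%. For a true AUC of 0.64 the reported mean runs from 0.66 to 0.73, and higher under strict correction.

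Little is lost in coverage for true AUCs of about 0.71 or more at unadjusted, uncorrected p<0.05, although the F and t readings still cut the implied sample size from 26 to 18–20 per group. Little is lost either for real markers of 0.64 or more at 50 per group and p<0.05. All figures rest on the stated assumptions, since the plan names no selection rule, family size or interval method. Confidence is high that validation is missing; the magnitude is a range. The change should be made, in proportion to an exploratory study.

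**What to change.** Amend the ROC paragraph of Section 12.1 in three parts.

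1. Keep the per-marker AUC and interval, but report them as apparent accuracy in the selection sample, not adjusted for selection. State that they will not be used to size the larger study (Sections 4.1 and 12.2) or quoted as diagnostic accuracy until estimated in new participants.
2. Where selection follows a stated test and threshold, add a repeated 5-fold cross-validated AUC, with selection and direction redone in each training set. Count a fold that selects nothing as 0.5 and report how often this happens. State that the result is the average accuracy of the markers the rule selects, not of any one marker. Take its interval from a bootstrap of the whole procedure, keeping copies of a participant in one fold, and state that it may fall below nominal coverage.
3. Markers chosen by Working Group judgement (Section 12.3) get the apparent label only, because that step cannot be rerun within folds.

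Part 2 was checked by simulation at 20 per group with 200 markers: none real, or 20 real at d = 0.5 or d = 0.8.

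| Threshold | Apparent AUC | True mean of selected | Cross-validated |
|---|---|---|---|
| p<0.05 | 0.707 / 0.718 / 0.737 | 0.500 / 0.559 / 0.630 | 0.495 / 0.553 / 0.623 |
| p<0.001, runs with a hit | 0.806 / 0.818 / 0.827 | 0.500 / 0.612 / 0.705 | 0.546 / 0.594 / 0.688 |

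At p<0.001, 56%, 36% and 8% of folds were empty, and the null estimate still read about 0.05 high. In a smaller run with 100 markers, the bootstrap interval covered 88–92% at p<0.05 and 94–100% at p<0.001, where it was wide (SE 0.10–0.12).

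The cost is a few sentences and computing time. That was about half a minute on simulated markers, but will be more for connectivity, where regions of interest are themselves defined from the task data and may need redefining in each fold. Held-out folds contain only four participants per group. The downside is less favourable reported accuracy and no validated single-marker AUC from this study.

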# 12.2 Power analysis

The accrual ceiling for participants in the phenotyping and exercise stress arms of this study is 150 participants (50 per group) and dropouts will be replaced. The sample sizes were chosen based on convenience and equals about 1-2 participants per week. This is a phase I pilot study intended to explore a variety of clinical and biological data from the three different groups. For neuroimaging studies of somatosensory stimulation, it is estimated to require 12 subjects to achieve 80% power at the threshold of 0.05 to determine differences at the single voxel level for typical activations. The proposed sample size of 20 participants per group should be adequate for distinguishing group differences in fMRI activity during the proposed fatiguing tasks. The study is exploratory and its results will be used to estimate effect sizes to design a larger clinical study.

# 12.3 Analytic Plan

To analyze the vast, multidimensional data collected in this protocol, the research team has organized four Working Each Working Group has been assigned a postbaccalaureate IRTA to assist in organization and with conducting a literature review. Groups to focus on four central themes: Clinical, Pathophysiology, Immunology, and Bioenergetics:

Clinical: [name] (Chair)

Data for analysis:

- Life Narratives
- Medical History
- Physical Exam
- Clinical laboratory measurements of blood and urine
- Neuropsychological Testing data
- SCID 5
- Patient Reported Outcome Measures
- Polysymptom Interview
- Activity Card Sort
- Cardiopulmonary Exercise Test
- Clinical Tilt Table Result
- Clinical Sleep Study Result
- Muscle Strength Grip Testing
- Nutritional data
- Microbiome
- ME/CFS Criteria Adjudication

Pathophysiology: [name] (Chair) Data for analysis:

- Neurological exams
- Structural Brain MRI
- Functional Brain MRI (Resting State, Diffuse Tensor Imaging, Hand Grip Task, Math Task)
- Dynamic Tilt-table Study data
- Single time point blood and CSF catecholamines measures

- 24 Hour Holter monitor data
- Overnight sleep EEG data
- Neuropsychological Testing data
- Transcranial Magnetic Stimulation data
- Salivary Cortisol measures (morning, afternoon, evening)
- Patient Reported Outcome Measures
- Cutaneous small fiber measurements of skin

Immunology: [name] and [name] (Co-chairs) Data for analysis:

- Clinical laboratory measures of inflammation
- Brain MRI with gadolinium
- Somalogic proteomics on blood and CSF
- Flow cytometry on blood and CSF
- RNASeq on PBMCs
- GDF-15 measures
- Muscle biopsy pathology (limited)
- Muscle RNASeq
- NK Cell functional assay
- Tryptase
- Toxicity studies on PBMCs
- Metabolomics of plasma and CSF
- Iron levels of CSF
- Exosomes of plasma
- Neurofilament analysis of plasma and CSF

Bioenergetics: [name] (Chair)

Data for analysis:

- Metabolic Chamber
- Physical Activity Monitoring
- DEXA measurement
- Dietary History and Food Records
- Cardiopulmonary Exercise Test
- RNASeq on PBMCs
- Seahorse mitochondrial assay on PBMCs
- Muscle Strength Testing
- Muscle biopsy pathology(limited)
- Muscle RNASeq
- Limited mitochondrial genetics data
- Metabolomics of plasma and CSF
- Microbiome

Each Working Group will begin by performing a literature review of their topic to ascertain the state of the ME/CFS field and guide their analyses. Analyses will be performed to both interrogate published findings to determine reproducibility and to make novel insights. Group members will first analyze the data that they are responsible

CNS IRB Protocol Template (2.5.15)

for collecting as part of the protocol. These individual data analyses will each be appropriate for the type of data collected and performed by Working Group members with experience in analyzing the data. Each Working Group will meet periodically to present their findings to each other, discuss issues of honing analyses, the need to expand data collection or perform additional experiments, identify areas of data consilience, and assemble a general consensus of how to interpret the results.

Once each Working Group completes its analysis and evaluation of the data, a series of combined Working Group meetings will be convened. Each Working Group will present their methods and results to each other. Break-out sessions will be organized that will mix the members of the Working Groups together to discuss how findings in one domain may relate to those in other domains. An open discussion for all Working Group members will be conducted to discuss issues of honing analyses, the need to expand data collection or perform additional experiments, identify areas of data consilience, and assemble a general consensus of how to interpret the results.

With the analyses of each Working Group completed, the research team will identify computational biologist collaborators to determine how to appropriately apply network analytics and machine learning approaches to the combined dataset. The goal of such analysis would to be elucidate observable linkages between the four research themes. These linkages would be areas of high interest in generating new hypotheses and also suggest potential therapeutic targets for future interventional studies.

These Working Groups have already been initiated to perform an interim analysis on the ME/CFS and HV cohorts completed as of October 2020.

# 13 Human Subjects Protection

# 13.1 Subject selection

Subject selection will be equitable among eligible participants. ME/CFS is reported to happen most commonly in persons aged 40-59. Increasing age also has significant effects of both on the experience of daily fatigue and on brain physiology. For this reason, individuals over the age of 60 will be excluded. Several of the neurocognitive instruments being used in this protocol require a 7th grade education for proper administration. These include the MMPI2, the Controlled Oral Word Association, and Grooved Pegboard tests. For this reason, persons with less than a 7th grade education will be excluded.

